NCT02772302 Study Title: Feasibility Study of the mindBEAGLE Device in Patients with Disorders of Consciousness or Locked-In Syndrome Version Date: February 27, 2018

PARTNERS HUMAN RESEARCH COMMITTEE DETAILED PROTOCOL

Feasibility Study of the mindBEAGLE Device in Patients with Disorders of Consciousness or Locked-In Syndrome

Study Investigators:

[name] (Principal Investigator) [name], PhD [name], PhD [name] [name] [name], BS [name]

Version Date: February 27, 2018

I. Background and Significance

Estimates of diagnostic error among clinicians who treat persons with disorders of consciousness (DOC) are consistently reported to be approximately 40% (Andrews *et al.*, 1996; Childs *et al.*, 1993; Schnakers *et al.*, 2009). The absence of a "gold standard" for consciousness is a major driver behind this problem. Behavior, as assessed by expert clinicians, is the standard metric relied upon to judge level of consciousness but, in practice, is a poor proxy for consciousness. Behavioral signs of conscious awareness may be too subtle to detect reliably. Conversely, reflexive or random behaviors may be misjudged as voluntary. Electroencephalography (EEG) offers potential for the development of relatively inexpensive, simple, compact systems that can be readily deployed at bedside to detect conscious processing in DOC patients.

Similarly, there is a small set of patients for whom speech and movement are severely impaired, but cognition remains intact. These patients, some of whom have LIS, need better methods of communication with their clinicians, family, and friends.

Over the last two decades, there has been considerable research into event-related EEG responses (ERs) (Chatelle *et al.*, 2012). This growing literature suggests that EEG-based paradigms may be employed to investigate cognition in severely brain-injured individuals who lack the capacity for speech and active movement (Chatelle *et al.*, 2012; Cruse *et al.*, 2011; Lule *et al.*, 2013; Schnakers *et al.*, 2008). Indeed, if conscious awareness could be identified for individual patients with high accuracy, this would contribute important information to early clinical decision making on a wide variety of medical and surgical issues. Similar EEG techniques can be used to enable communication for people with locked in syndrome (LIS) or other difficulties with communication.

Even if ERs may offer a means to assess human information processing capabilities in the absence of overt behavior, the extent to which DOC patients are capable of processing even simple instructions is unclear, and prognostic indicators predicting the functional outcome of these patients are limited and non-specific. Some studies have demonstrated preserved ERs in coma, vegetative states, and minimally conscious state (Cruse *et al.*, 2011; Cruse *et al.*, 2012; Perrin *et al.*, 2006; Schnakers *et al.*, 2008; Steppacher *et al.*, 2013), but due to the small number of investigated cases and frequent lack of outcome documentation, their clinical and prognostic significance is currently unclear. Almost none of these studies focus on the initial period after injury.

The presence of ERs after brain damage, in particular endogenous ERs that appear relatively late after stimulus onset and reflect more complex cognitive operations, may predict subsequent recovery of consciousness and communicative abilities (Steppacher *et al.*, 2013). These ER components depend on the synchronized activity of multiple brain regions, which may be critical for conscious awareness.

A new, portable technology called "mindBEAGLE" has been developed by an Austrian neurotechnology company with the intent of providing simple and rapid assessment of the presence of auditory and somatosensory evoked EEG responses in people with DOC or LIS. We propose to evaluate the feasibility of this no-to-minimal risk technology with up to 20 inpatient participants at MGH. The EEG data collected from this system will be correlated with behavioral assessments of consciousness using the Coma Recovery Scale-Revised (CRS-R), which has been shown to optimize sensitivity for detecting conscious awareness in patients with DOC and LIS. The same system will be tested in up to 20 healthy controls to provide baseline validation of the technology.

II. Specific Aims

The primary aims of this study are:

- 1) To determine the **feasibility** of deploying mindBEAGLE, a portable, bedside EEG-based system, in the Neurosciences Intensive Care Unit in patients with DOC or LIS;
- 2) To determine if mindBEAGLE neurophysiologic markers of cognitive function correlate with bedside behavioral assessments of consciousness;
- 3) To determine if mindBEAGLE can serve as an assistive communication device for people with LIS.

III. Subject Selection

HEALTHY PARTICIPANTS (n = 20)

Inclusion Criteria

- Minimum age: 18
- Capacity to provide informed consent
- Fluent in English

Exclusion Criteria

• History of developmental, neurologic, or major psychiatric disorder resulting in functional disability

INPATIENT PARTICIPANTS (n = 20)

Inclusion Criteria

- Age 18 80
- Fluent in English
- For DOC only:

- Surrogate decision-maker (whomever is consenting for clinical procedures, as described in the consent procedures below) available to provide informed consent
- History of severe acquired brain injury with loss of consciousness
- Diagnosis of coma, vegetative state, minimally conscious state or confusional state
- Inpatient at Lunder 6 (NeuroICU at MGH)
- For LIS only:
 - \circ Ability to maintain wakefulness for ~30 minutes without sedative medication, as assessed by nursing staff.
 - \circ Ability to remain off intravenous sedative medication for ~60 minutes.
 - Inpatient at Lunder 6 (NeuroICU at MGH).
 - o (see consent procedures below)

Exclusion Criteria

- Prior history of developmental, neurologic, or major psychiatric disorder resulting in functional disability
- Evidence of uncontrolled seizure disorder
- Patients for whom EEG leads are contraindicated
- Injury preventing the placement of surface EMG-type leads on the hands or back.

IV. Subject Enrollment

We plan to enroll a total of 20 patients treated at Massachusetts General Hospital (MGH) for DOC or LIS. Eligible subjects who meet the inclusion criteria will be identified by study staff at MGH, and consent will be obtained from the patient's surrogate with assent from the patient if possible. We also plan to enroll 20 healthy control subjects. These healthy control subjects will be identified with a recruitment flier that will be posted at MGH. The exact text from this recruitment flier will also be posted on the Partners clinical studies website clinicaltrials.partners.org and circulated via the *All User MGH* email list.

V. Study Procedures

Subject Screening – Subjects will be screened by study staff using the daily Lunder 6 NeuroICU inpatient list.

Consent - Informed consent will be obtained from all subjects (or their surrogates) by study staff prior to all study procedures. Informed consent for participation may be obtained from a representative (surrogate) for those incapable of providing informed consent. The following categories of surrogates in order of preference may provide consent in writing on behalf of potential subjects incapable of providing informed consent on their own behalf:

- i) court appointed guardian with specific authority to consent to participation in research or authority to make health care decisions for a class of diagnostic and therapeutic decisions inclusive of the proposed research
- ii) health care proxy/person with durable power of attorney with specific authority for making health care decisions inclusive of the proposed research
- iii) spouse, adult child, or other close family member who knows the subject well and has been involved in their care

Should surrogate consent be obtained, the investigator will document the relationship of the surrogate to the subject in the research record. The investigator obtaining consent will also ensure that the surrogate understands that her/his decisions should be based on the potential subject's own views when s/he had the capacity to express them ("substituted judgment"). Subject assent will also be a requirement for participation in the research unless the subject is incapable of providing it, given her/his medical condition.

In order to minimize the possibility of patients and/or surrogates feeling obligated to participate in research in the event that one of the investigators is also their physician, a physician colleague or research nurse not involved in their care will initially explain the study to potential subjects. We will also offer patients and/or surrogates the opportunity to review the consent form privately and be contacted once they have been able to do so.

The investigator obtaining consent will explain in detail the protocol of the study, its purpose and potential benefits to society. Surrogates and subjects will be informed about minimal risks of EEG. Subjects will be informed that if they feel uncomfortable with the study, they can choose to terminate the study at any time. Surrogates and subjects will be informed that their refusal to participate in the study or choosing to terminate it at some point will have no effect on care and treatment received by them at any Partners institution (i.e. Spaulding, MGH, etc.) now or in future. Informed consent clearly states that subjects and surrogates may choose to terminate the study at any time. Surrogates and subjects will be informed that their personal information will be protected as per the HIPAA guidelines. Surrogates and subjects will have as much time as they wish to consider participation in the study. Although subjects must be fluent in English in order to participate in the study, there may be circumstances where a subject is consented to the study by a non-English speaking surrogate. In these circumstances, the consenting Investigator will utilize MGH Interpreter Services, and the consent process will be documented on the MGH IRB-approved short form consent document and full English-version consent form, in compliance with PHS IRB.

Organization of the study – Patients with DOC or LIS will be evaluated once, although the technology may be made available to them during their inpatient stay if it is found to provide a more reliable method of communication than the patient's current method (as previously determined by a nurse, physician, or speech-language therapist). A behavioral assessment will be performed at the time of the mindBEAGLE EEG assessment.

Healthy subjects will only be assessed once and will be considered as a control group.

Clinical data collection - Demographic and clinical data recorded in the medical record at the time of admission will be collected in accordance with the common data elements recently proposed by the interagency committee of the TBI Common Data Element Project, including age, gender, injury mechanism, admission Glasgow Coma Scale (GCS) score, CT findings, duration of coma, and brainstem function (e.g. pupillary and corneal reflexes). We will also record standard clinical data about level of consciousness (e.g. CRS-R score), severity of LIS (e.g. cranial nerve and extremity motor examination), and level of functional recovery (e.g. Disability Rating Scale score).

EEG - Each subject will be given an EEG, which will utilize the mindBEAGLE system in order to attempt to assess level of consciousness. The EEG will last up to 120 minutes and the subject will be sitting down or lying down. We may also play recordings of spoken language or music via headphones, or we may ask the subject to perform certain tasks, like saying a word to herself or imagining that she is tapping her fingers. We will give the subject specific instructions about these tasks during the EEG.

Neurobehavioral testing – The primary behavioral measure of level of consciousness will be the CRS-Rderived diagnosis of recovery of consciousness, which will allow for classification of each patient as being in coma, vegetative state, minimally conscious state, emerged from minimally conscious state, confusional state, or in a state of fully recovered consciousness. This assessment will be performed by study staff at MGH. The entire neurobehavioral assessment will last up to 60 minutes.

Neurobehavioral (level of consciousness) data will be shared with the subjects, their surrogates, or their outside physicians, at the subject's and/or the surrogate's request, since these data come from well validated assessment tools that are routinely used in clinical practice. Furthermore, the results from these tests can be compared to prior results from these same tests, which are routinely performed as part of clinical care at MGH.

Sharing EEG results with families and treating clinicians

After extensive consideration of the ethical implications of sharing or not sharing the mindBEAGLE EEG data with the patient's family (or non-family surrogate decision-maker) and treating clinicians, our team has reached the following consensus: we believe that the most appropriate course of action from an ethical standpoint is to make the results of these tests available to the patient's surrogate decision-maker AND clinical team, at the request of the surrogate decision-maker. In reaching this consensus, we considering the following points:

- While tools such as the mindBEAGLE system have not been validated as prognostic tools in large, randomly controlled clinical trials, there are preliminary studies suggesting that stimulus-based EEG techniques may be able to detect signs of cognitive awareness that cannot be detected on bedside exam (Cruse et al. 2011). On the one hand, we are hesitant to share data from tests that have not been fully validated. However, we also believe that it would not be appropriate to withhold critically important information about functional activation of brain networks, especially since this information could potentially impact the surrogate's decisions about goals of care as well as the clinical team's impression of the prognosis.
- Consistent with our team's consensus opinion, experts in the field of DOC research recently published a manuscript supporting the dissemination of EEG results to families (Graham *et al.*, 2015). The authors of this manuscript invoke the same rationale articulated above. There is thus an emerging consensus in the field that sharing these results is the ethically appropriate course of action.

We therefore believe that sharing the mindBEAGLE results is ethically justifiable, given that withholding such information might prevent families and clinicians from making a fully informed formulation of the patient's prognosis.

VI. Biostatistical Analysis

In addition to determination of feasibility of deployment of the mindBEAGLE system in the ICU, we will test correlations between mindBEAGLE neurophysiologic markers of cognitive function with CRS-R diagnosis, as well as with EEG biomarkers of consciousness. For example, univariate correlations will be tested using Pearson's and Spearman's correlation tests. We will also attempt to determine whether mindBEAGLE neurophysiologic markers are stable and informative enough to use the system as an assistive communication device.

VII. Risks and Discomforts

The EEG involves one routine EEG test, for which there are no known or foreseeable risks. Medical risk to subjects during the paradigm is not anticipated. There is a risk of minor superficial skin irritation. However, it is infrequent, easily treated and fully reversible.

Study activities will be deferred or discontinued if subjects become medically unstable prior to, or during, procedures. Continuation will be dependent upon consensual approval of the participant or surrogate and the research team.

There are no anticipated medical risks associated with the neurobehavioral/physical examinations that will be conducted in this study. Some exams sometimes include brief application of noxious stimulation to the finger and/or toenail beds to assess motor responses in the absence of command-following. Discomfort typically lasts less than 10 seconds and resolves completely.

There are no other known risks from participation in this study.

VIII. Potential Benefits

For the participants, there is no direct benefit. However, it may result in significant societal benefit, as the development of new diagnostic tools may help guide clinical management for physicians and families of patients with DOC or LIS.

IX. Monitoring and Quality Assurance

All data and safety monitoring will be done by the Principal Investigator of this study. Adverse events will be reported to the IRB within 24 hours by fax, and within 10 days by interoffice mail, as per IRB regulations. A licensed physician will be available in the ICU to address any unforeseen complications.

Any unanticipated adverse events involving risk to human subjects will be reviewed by the Principal Investigator and will be quickly reported to the Human Research Committee within the required time frame and to all participating investigators by [name] according to the Partners Human Research Committee guidelines.

Monitoring of the study data itself will be performed by the investigators at MGH, who have an active interest in the results of the study.

References:

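### Section V does not keep the CRS-R rater from the mindBEAGLE output, or the EEG reader from the CRS-R result, so the Aim 2 correlation may be distorted, most plausibly upward

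*Combined protocol and SAP*

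**What the plan says.** Section II makes this a primary aim: "To determine if mindBEAGLE neurophysiologic markers of cognitive function correlate with bedside behavioral assessments of consciousness". Section VI repeats it as an analysis: "we will test correlations between mindBEAGLE neurophysiologic markers of cognitive function with CRS-R diagnosis". Pearson and Spearman tests are offered there as examples, with no alpha, target correlation or power.

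Under Organization of the study, Section V evaluates each patient once and adds: "A behavioral assessment will be performed at the time of the mindBEAGLE EEG assessment". Under Neurobehavioral testing it says of the CRS-R: "This assessment will be performed by study staff at MGH". The CRS-R diagnosis has six categories.

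The EEG paragraph of Section V does not name who runs or reads the mindBEAGLE recording, or say how a marker is derived from it. No section sets the order of the two tests, masks either result, or requires one to be recorded before the other is known.

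Three other places bear on what staff may know:
- For DOC patients, Section III lists as an inclusion criterion "Diagnosis of coma, vegetative state, minimally conscious state or confusional state".
- Section V notes that the same behavioral tests are part of routine care at the hospital.
- Section V makes EEG results available to the surrogate and the clinical team when the surrogate asks, with no stated hold until the CRS-R is final.

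**The concern.** A correlation between two measurements supports Aim 2 only if each is obtained without knowledge of the other. The Background itself says that behavioral signs can be subtle and that reflexes can be taken for voluntary acts, so the CRS-R involves judgment. If the rater has seen the EEG output, or the EEG reader knows the CRS-R result, part of the observed association may come from the assessor. Neither Pearson's nor Spearman's test can separate that part from a true association.

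Each patient is evaluated once, so no later study rating is planned that could reveal or correct the influence. Aims 1 and 3, feasibility and assistive communication, do not depend on this point.

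**Working it through.** **No plan figure to reproduce.** The documents give 20 patients (Section IV; the Background says up to 20) and no alpha, power or expected correlation. What follows shows only how sensitive the result is. Drift, exposure and alpha are assumptions.

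**Inputs.** From the documents: n = 20; six CRS-R categories (Section V). Assumed: two-sided alpha 0.05; drift b of 0.1 to 0.4 SD; a share of exposed ratings of 100%, 50% or 25%; six categories equally likely when there is no drift.

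**Model, EEG result influencing the CRS-R.** Let E be the standardized marker and C the latent rating without influence, with correlation rho. An exposed rating becomes C + b × E and is then cut into six categories. Spearman's test uses the t approximation, with at least 50,000 simulated trials per setting.

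**No true association (rho = 0), chance of p < 0.05:**

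| Drift b | All exposed | Half | A quarter |
|---|---|---|---|
| 0 | 5.2% | 5.2% | 5.2% |
| 0.1 | 6.7% | 5.5% | 5.3% |
| 0.2 | 11.8% | 6.6% | 5.5% |
| 0.3 | 20.7% | 8.7% | 5.9% |
| 0.4 | 31.8% | 11.3% | 6.5% |

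With all ratings exposed, the mean Spearman coefficient is 0.089, 0.175, 0.258 and 0.334 at the four drifts. A drift of -0.2 mirrors +0.2: mean -0.176, p < 0.05 in 11.9%. With 12 patients, all exposed, the rates are 6.1%, 8.9%, 13.5% and 19.6%.

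**True latent correlation 0.5, n = 20, chance of p < 0.05:**

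| Exposed | b = -0.2 | b = 0 | b = +0.2 |
|---|---|---|---|
| All | 26% | 56% | 80% |
| Half | about 39% | 56% | about 69% |
| A quarter | about 48% | 56% | about 62% |

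Assigning exposure at random patient by patient gives 40% in place of 39%. With all exposed, the mean Spearman coefficient is 0.297, 0.455 and 0.575 across the three drifts.

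**Reverse pathway, CRS-R result influencing the marker** (marker = N(0,1) + b × standardized category, rho = 0, n = 20): 7.0%, 12.8%, 22.3% and 35.6% if all are exposed; 5.2% to 6.8% if a quarter are.

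**Cross-check by formula** (continuous scale, all exposed): observed r = (rho + b) / √(1 + b² + 2 × b × rho).
- rho = 0, b = 0.2: 0.2 / √1.04 = 0.196. Fisher's z with n - 3 = 17 gives p < 0.05 in 13%.
- rho = 0, b = 0.4: 0.4 / √1.16 = 0.371, giving 36%.
- rho = 0.5, b = 0.2: 0.7 / √1.24 = 0.629, giving 86%.
- rho = 0.5, b = -0.2: 0.3 / √0.84 = 0.327, giving 29%, against 62% at b = 0.

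The pattern agrees with the simulation; cutting the rating into categories lowers the correlations somewhat. At n = 20 the critical |r| is 0.44, so a modest shift can decide whether Aim 2 appears to be met.

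**The case against.** The strongest reply is that this argues from silence. Section V does not say that the CRS-R follows the EEG, that one person does both, or that EEG output is read before the CRS-R is scored. That stands: a reader might infer that staff will be unmasked, and the documents do not support that. They only fail to prevent it. Testing on one occasion is not a fault either, since it limits change in the patient's state between the two tests.

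The size is also assumed. The large figures need every rating exposed; with a quarter exposed, the false-positive rate barely leaves 5%. This stands too, which is why the full exposure range is shown.

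On direction, a reader might infer that the investigators expect EEG and bedside findings to disagree, so that deflation is as likely as inflation. Section V goes less far. It reports preliminary studies suggesting that "stimulus-based EEG techniques may be able to detect signs of cognitive awareness that cannot be detected on bedside exam", and it voices hesitation about tests that are not fully validated. Deflation is possible on that basis, but drift toward agreement is the more natural worry.

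Two mitigating points count in part. Section V describes the behavioral tools as validated, but validation does not stop expectation from affecting a rating. If mindBEAGLE output is scored automatically, the concern about EEG reading shrinks. The documents do not say that it is, and the influence of EEG output on the CRS-R rater would remain.

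Finally, this is a small feasibility study with no success threshold. That limits the weight of the point but does not remove it, because Section II lists the correlation among the primary aims.

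**Conclusion.** The point holds as a gap in the plan. Both measures behind a primary aim are obtained at one evaluation, and nothing keeps either from the assessor of the other or records which came first. The correlation may be distorted, with inflation the main concern and deflation possible. A reader might go further and conclude that the Aim 2 result will be inflated, or by how much. The documents support neither conclusion: direction and size depend on how many ratings are exposed and how far knowledge moves them, and no document gives either.

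Under the assumed drifts, the consequence runs from almost nothing (a quarter exposed) to a false-positive rate of about 32% (all exposed, drift 0.4 SD). Where a latent correlation of 0.5 exists, the chance of p < 0.05 could move from 56% to as low as 26% or as high as 80% with full exposure at drift -0.2 or +0.2. The change is worth making because any influence cannot be removed afterwards and preventing most of it is cheap.

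**What to change.** Add a paragraph to Section V stating that:

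1. The CRS-R is scored, time-stamped and locked before its rater sees any mindBEAGLE output. Where one person does both tests, either the CRS-R is completed and locked first, or the exposure is recorded and reported as a limitation.
2. The markers used for Aim 2 are defined in advance and extracted from ID-coded files without access to the CRS-R result.
3. The order of the two tests, and who performed each, are recorded for every patient.

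Say also that, once the CRS-R is locked, results remain available on request and the device remains available for communication, both as Section V already provides. Release need not wait for offline marker extraction, so the sharing policy is kept.

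**Cost.** No new assessor and no added testing: one paragraph, a time stamp on the CRS-R form and two recorded items. The real work is defining the markers, which Section VI does not do at present. There is a brief hold on EEG results until the CRS-R is locked. Protection is only partial, because staff may know the entry diagnosis and earlier routine behavioral results.

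### Section VII closes by denying any further risk of participation, although Section V lets individual results from an incompletely validated test reach people deciding goals of care

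*Combined protocol and SAP*

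**What the plan says.** Section VII lists minor skin irritation from the EEG and brief discomfort from noxious stimulation during the behavioural examination, then closes: "There are no other known risks from participation in this study".

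The consent text in Section V describes the risk content of the discussion in one sentence: "Surrogates and subjects will be informed about minimal risks of EEG".

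The subsection of Section V on sharing EEG results makes a patient's mindBEAGLE results available to the surrogate and the clinical team if the surrogate requests them. It acknowledges that "we are hesitant to share data from tests that have not been fully validated". It sets against this that "this information could potentially impact the surrogate's decisions about goals of care as well as the clinical team's impression of the prognosis", and concludes that sharing is justified.

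On the healthy participants, Section I says "The same system will be tested in up to 20 healthy controls to provide baseline validation of the technology" and Section V says "Healthy subjects will only be assessed once and will be considered as a control group". In Section VI the planned analysis is feasibility, correlation ("we will test correlations between mindBEAGLE neurophysiologic markers of cognitive function with CRS-R diagnosis", and with EEG biomarkers), and suitability for communication. Healthy participants are not mentioned there.

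**The concern.** Section V treats a disclosed result as something that can change what a surrogate decides and how the clinical team sees the prognosis. It also says the test behind that result is incompletely validated. If a correct result can move such a decision, so can a wrong one. A false-negative or false-positive result reaching decision-makers is then a consequence of participation that the investigators can foresee, and the closing sentence of Section VII says there is none of that kind.

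At stake is what surrogates are told before they agree, and what accompanies a result when they ask for it. A reader who relies on the risk section alone would not learn of the hesitation recorded in Section V.

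The control group bears on this to a smaller extent. The controls are enrolled to validate the technology, but the plan does not say what will be reported about them. The study therefore has no planned figure showing how often the system fails to find the expected response in people known to be conscious.

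**Working it through.** **Main point: comparison of the passages.** No arithmetic applies, because the documents state no error rate for the device.

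1. Is an individual result disclosed? Yes, on the surrogate's request, to the surrogate and the clinical team (Section V, sharing subsection).
2. Is the test treated as validated? No. The same subsection records the hesitation quoted above. Section I adds that the clinical and prognostic meaning of these responses is still unclear. By contrast, Section V justifies sharing the behavioural results on the ground that those tools are well validated.
3. Is an effect on decisions foreseen? Yes, on goals of care and on the impression of prognosis.
4. Is a repeat research assessment planned that could correct a misleading result? None is described; patients are evaluated once (Section V, organization of the study).
5. Is the risk named in Section VII? No. Its two specific items are skin irritation and brief discomfort, and its last sentence covers participation as a whole.
6. Is it named in the consent paragraph? No. The only risk content described there is that of the EEG.

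Steps 1 to 3 establish a foreseeable risk; steps 5 and 6 show that it is not carried over.

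**Secondary point: what a control summary could show.** The plan has no figure to reproduce. The number of controls is 20 (Section III; Section I says up to 20). The counts of controls with the expected response are assumptions. With x misses among n = 20, the exact (Clopper-Pearson) 95% limits are:

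- lower limit = 2.5% quantile of Beta(x, n − x + 1), or 0 if x = 0;
- upper limit = 97.5% quantile of Beta(x + 1, n − x). For x = 0 this equals 1 − 0.025^(1/n).

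For x = 0: 1 − 0.025^(1/20) = 1 − 0.832 = 0.168.

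| Assumed responders | Miss rate | Exact 95% interval |
|---|---|---|
| 20/20 | 0% | 0 to 16.8% |
| 18/20 | 10% | 1.2 to 31.7% |
| 15/20 | 25% | 8.7 to 49.1% |

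The intervals widen if fewer than 20 controls are tested. Healthy controls give no information on false positives, since all of them are conscious.

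**The case against.** The strongest reply is that the protocol has already dealt with the matter. Disclosure happens only on request, and Section V openly weighs incomplete validation against the harm of withholding information. The investigator is also to explain the study in detail at consent. This disposes of any claim that the issue was ignored. It does not remove the conflict: deciding that a risk is worth taking is a reason to list it, and Section VII says no further risk is known.

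A reader might infer that the sentence "The EEG involves one routine EEG test, for which there are no known or foreseeable risks" is itself contradicted by the sharing policy. The text does not support that. The sentence concerns the EEG procedure and is followed by remarks on medical risk during the paradigm and on skin irritation. The conflict lies with the closing sentence, which speaks of participation.

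A reader might also infer that surrogates are not told of this risk. That cannot be judged, because the consent form is not among the documents available and the consent paragraph need not be exhaustive.

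On the controls, it is fair to say that Section VI is brief, suits a feasibility study and gives its correlation tests only as examples. Aim 3 also directs attention to patients with locked-in syndrome, so conscious patients are not overlooked. The documents do not show that control data will go unanalysed, only that no analysis of them is written down. The plan also has no yes-or-no response rule, and its correlations would suit graded markers, so a miss rate has no meaning until a criterion is set for each paradigm.

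**Conclusion.** The main point stands. The closing sentence of Section VII and the risk wording in the consent paragraph do not agree with the sharing subsection of Section V, and a foreseeable risk is missing from the risk section as written. The correction should be made: it affects what surrogates are told about a result that may bear on goals of care. It concerns any of the 20 planned patients whose result is requested. How often a result would mislead cannot be stated, because the documents give no error rate.

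The finding does not say that results should be withheld; the documents give a reasoned case for sharing.

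The control summary is a separate, lower-priority gap. The 16.8% limit depends on an assumed 20 of 20 responders and shows what a sample of that size can exclude. It is not an estimate for this device, nor for ICU patients, and an absent evoked response in one paradigm is not the same as missed consciousness.

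**What to change.** Reconcile the three places:

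- **Section VII:** replace the closing sentence with one that names a false-negative or false-positive disclosed result as a foreseeable risk of participation.
- **Section V, consent:** add this risk to what surrogates and subjects are told, and check that the consent form agrees.
- **Section V, sharing of EEG results:** state that any released result carries the protocol's own statement that the test has not been fully validated.

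Whether results are shared, and how they are used clinically, remains with the study team.

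As a lower-priority addition to Section VI, fix the criterion for the expected response in each paradigm before patient results are reviewed. Then report, for each paradigm, the proportion of healthy controls meeting it with an exact 95% confidence interval.

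The cost is wording and one descriptive summary, with no added participants or procedures. The downsides are a less favourable risk statement and wide intervals. Because no testing order is stated, there may also be no control figure for patients assessed before the controls.
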